13.5 Analysis of Exploratory Objectives COHORT A AND B

- Explore the relationship between tumor CSF1 gene signature by RNA analysis and response to combination treatment of nivolumab and ipilimumab.
- Explore the relationship of potential biomarkers associated with disease control of ULMS treated with combination treatment of nivolumab and ipilimumab by evaluating biomarkers within the tumor microenvironment and the periphery.

We will use non-parametric tests to assess the relationships listed above and response to combination treatment of nivolumab and ipilimumab. Logistic regression will be used for response measured outcomes. Outcome relationships will be largely explorative and descriptive.

13.6 Reporting and Exclusions

13.6.1 Evaluation of Toxicity

All patients will be evaluable for toxicity from the time of their first treatment with nivolumab and ipilimumab. All patients who receive at least one dose of nivolumab and ipilimumab will be included in the toxicity analysis. This includes participants who receive study drug and are ultimately deemed ineligible.

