1.2 Secondary Objectives

Secondary Objectives:

- To evaluate the toxicity of nivolumab in patients with advanced ULMS.
- To evaluate the toxicity of nivolumab in combination with ipilimumab in patients with advanced ULMS.
- To evaluate the progression-free survival of ULMS treated with nivolumab.
- To evaluate the progression-free survival of ULMS treated with nivolumab in combination with ipilimumab.
- To explore the relationship between PDL1, PD1 in infiltrating lymphocytes and PD2 status in archival tumor, and pre/post treatment biopsies in a minimum of 10 patients.

Exploratory Objectives:

- To explore the relationship between general immune response and specific markers of immunomodulation and response to nivolumab.
- To explore the relationship between tumor inflammatory gene signature and response to nivolumab in archival material.

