5.1.1 COHORT A (nivolumab alone)- Closed to Accrual

Cohort A opened for accrual on 13-May-2015; accrual to this cohort was completed on 21-Oct-2015. All participants in Cohort A received Nivolumab monotherapy as per the below dosing instructions.

Nivolumab will be given every two weeks (± 2 days) at a dose of 3 mg/kg. Patients may be dosed no less than 12 days from the previous dose of drug.

The dosing calculations should be based on the actual body weight. If the patient's weight on the day of dosing differs by $>10\%$ from the weight used to calculate the original dose, the dose must be recalculated. Actual body weight at each visit may be used to calculate dose, as per institutional standard. All doses should be rounded as per institutional standard. There will be no dose modifications allowed.

Nivolumab is to be administered over an approximately 60-minute IV infusion, using a volumetric pump with a 0.2-1.2 micron in-line filter at the protocol-specified dose. The drug can be diluted with 0.9% normal saline for delivery but the total drug concentration of the solution cannot be below 0.35 mg/mL. It is not to be administered as an IV push or bolus injection. At the end of the infusion, flush the line with a sufficient quantity of normal saline. .

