11 MEASUREMENT OF EFFECT

11.1 Antitumor Effect – Solid Tumors

For the purposes of this study, patients should be re-evaluated for response every 8 weeks (+/- 2 days). In addition to a baseline scan, confirmatory scans should also be obtained at least 4 weeks following initial documentation of objective response.

Response and progression will be evaluated in this study using the new international criteria proposed by the revised Response Evaluation Criteria in Solid Tumors (RECIST) guideline (version 1.1) [Eur J Ca 45:228-247, 2009]. Changes in the largest diameter (unidimensional measurement) of the tumor lesions and the shortest diameter in the case of malignant lymph nodes are used in the RECIST criteria.

All patients who receive at least one dose of nivolumab and ipilimumab each will be included in the toxicity analysis. This includes participants who receive study drug and are ultimately deemed ineligible.

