11.1.1 Definitions

Evaluable for toxicity. All patients will be evaluable for toxicity from the time of their first treatment with nivolumab and ipilimumab.

Evaluable for objective response. Only those patients who have measurable disease present at baseline, have received at least one cycle of therapy, and have had their disease re-evaluated will be considered evaluable for response. These patients will have their response classified according to the definitions stated below. (Note: Patients who exhibit objective disease progression prior to the end of cycle 1 will also be considered evaluable.)

Evaluable Non-Target Disease Response. Patients who have lesions present at baseline that are evaluable but do not meet the definitions of measurable disease, have received at least one cycle of therapy, and have had their disease re-evaluated will be considered evaluable for non-target disease. The response assessment is based on the presence, absence, or unequivocal progression of the lesions.

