13 STATISTICAL CONSIDERATIONS

13.1 Study Design/Endpoints

COHORT A - Study Design and Endpoints

This is a phase II two-stage clinical trial with a primary endpoint of objective response per RECISTS 1.1 among patients with advanced ULMS treated with nivolumab.

For the primary endpoint of overall response with a null hypothesis of 5% and an alternative hypothesis of 20% we would need 37 patients in a two-stage design with 12 patients in the first stage and 25 patients in the second stage. At the first stage analysis we will assess overall response, we will need to observe at least 1 response out of 12 patients to continue through the second stage. At the second stage we will assess overall response rate again, and we will need to observe at least 4 responses out of 37 patients to accept the treatment. The overall power for overall response rate is 90%. The overall type I error, the chance of incorrectly rejecting the null hypothesis is 9%. The probability of stopping at the first stage under the null hypothesis is 54%. The operating characteristics of this design are calculated using the exact binomial distribution. Subjects who continue treatment beyond initial investigator-assessed, RECIST 1.1-defined the initial progression event but may be designated as delayed responses for purposes of determining ORR and counted as responses for two stage designs.

Paired immediate pre-treatment and post- treatment biopsies will be obtained whenever possible in consenting patients, and in a minimum of 10 patients. If less than 10 patients have provided paired tumor biopsies, the remaining slots will give priority to obtain biopsies in the last group of 10 patients prior to completion of accrual. For the primary endpoint of overall response rate with the parameters as noted in section 13.1, a total sample size of 37 patients is needed in a two-stage design with 12 patients in the first stage and 25 patients in the second stage. A minimum accrual rate is expected to be 3 subjects per month. With a minimal accrual rate of 3 subjects per month, we expect the study enrollment to last approximately 13 months.

For Cohort A, 12 participants were accrued to the first stage. Since an objective response was not seen in the first stage of Cohort A, enrollment to the second stage did not begin.

COHORT B – Study Design and Endpoints

This phase II two-stage clinical trial will include patients with advanced ULMS treated with

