13.4 Analysis of Secondary Endpoints

COHORT A – SECONDARY ENDPOINTS

We will also assess toxicity in patients with ULMS treated with nivolumab. Among the first phase of 12 patients, there is at least 58% probability of observing one or more rare (7% true probability) events, and 83% probability of observing toxicities that have a true occurrence of at least 15%. Among the total cohort of 37 patients, there is at least 85% probability of observing one or more rare (5% true probability) events, and 95% probability of observing toxicities that have a true occurrence of at least 8%. With 37 treated patients, the maximum width of a 90% two-sided exact binomial confidence interval for any estimated adverse event proportion will be no wider than $\pm 14\%$.

Rate of Progression-free survival at 12 weeks with a null hypothesis of 20% and an alternative hypothesis of 40% at 12 weeks will be investigated. Patients lost to follow-up or deaths within 12 weeks will be counted as failures. The overall power for overall progression-free rate at 12 weeks is 87%, using the exact binomial distribution. The

operating characteristics of this design are calculated using a one-sided exact test with 10% type I error.

COHORT B – SECONDARY ENDPOINTS

Toxicity: Among the first phase of 8 patients, there is at least 57% probability of observing one or more rare (10% true probability) events, and 73% probability of observing one or more toxicities that have a true occurrence rate as low as 15%. Among the total cohort of 25 patients, there is at least 84% probability of observing one or more rare (7% true probability) events, and 93% probability of observing toxicities that have a true occurrence of at least 10%. With 25 treated patients, the maximum width of a 90% two-sided exact binomial confidence interval for any estimated adverse event proportion will be no wider than $\pm 18\%$.

Rate of Progression-free survival at 6 months with a null hypothesis of 18% and an alternative hypothesis of 40% at 6 months will be investigated. Patients lost to follow-up or deaths within 6 months will be counted as failures. The overall power for overall progression-free rate at 6 months is 85%, using the exact binomial distribution. The operating characteristics of this design are calculated using a one-sided exact test with 10% type I error.

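### The toxicity set requires a dose of both drugs, which leaves Cohort A with no patients and drops any Cohort B patient who never receives ipilimumab

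*Combined protocol and SAP*

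**What the plan says.** Three places define who counts for toxicity, and none is limited to a cohort.

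- Section 13.6.1: "All patients who receive at least one dose of nivolumab and ipilimumab will be included in the toxicity analysis".
- Section 11.1: "All patients who receive at least one dose of nivolumab and ipilimumab each will be included in the toxicity analysis".
- Section 11.1.1, repeated at the start of 13.6.1: "All patients will be evaluable for toxicity from the time of their first treatment with nivolumab and ipilimumab".

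Sections 11.1 and 13.6.1 add that treated patients later found ineligible stay in.

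Other parts of the plan assume a wider set.

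- Section 1.2 lists as a secondary objective: "To evaluate the toxicity of nivolumab in patients with advanced ULMS".
- Section 5.1.1: "All participants in Cohort A received Nivolumab monotherapy as per the below dosing instructions". Section 13.1: "For Cohort A, 12 participants were accrued to the first stage".
- Section 13.4 plans the Cohort A analysis ("We will also assess toxicity in patients with ULMS treated with nivolumab") on 12 patients in the first stage and 37 in total.
- For Cohort B, section 13.4 works from 8 patients in the first stage and from all treated patients in total: "With 25 treated patients, the maximum width of a 90% two-sided exact binomial confidence interval" is given as within ±18%.

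**The concern.** The rule conflicts with the rest of the plan in two ways.

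First, Cohort A patients never received ipilimumab. Taken literally, the rule empties the set for an objective the protocol still lists. Section 2.5 says that Cohort B was added by amendment, so this is probably combination wording applied to the whole protocol.

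Second, section 5.1.2 has nivolumab infused before ipilimumab in Cohort B. A patient can therefore start treatment, be harmed and stop before any ipilimumab is given. Section 5.8 describes such a case: a grade 3 or 4 reaction ends the nivolumab infusion at once. If she never receives ipilimumab she is outside the set, and the reason is the outcome being counted. The reported rate of that event is then too low. Rates of events she did not have rise slightly, because the denominator shrinks. A patient who reacts but later receives ipilimumab stays in.

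The toxicity rule is also stricter about exposure than the response rule. Section 13.6.2 keeps patients in the response analysis despite incorrect drug administration.

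**Working it through.** **1. Which denominator do the planned figures use?** The chance of seeing at least one event is 1 − (1 − p)^n. Precision is the largest half-width of the 90% exact (Clopper-Pearson) interval over all possible counts. Rates, sample sizes and stated values are from section 13.4.

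| Cohort | n | True rate | Stated | Recomputed |
|---|---|---|---|---|
| A | 12 | 7% | 58% | 58.1% |
| A | 12 | 15% | 83% | 85.8% |
| A | 37 | 5% | 85% | 85.0% |
| A | 37 | 8% | 95% | 95.4% |
| A | 37 | half-width | ±14% | 14.5% |
| B | 8 | 10% | 57% | 57.0% |
| B | 8 | 15% | 73% | 72.8% |
| B | 25 | 7% | 84% | 83.7% |
| B | 25 | 10% | 93% | 92.8% |
| B | 25 | half-width | ±18% | 17.7% |

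All the Cohort B figures reproduce with 8 and 25, that is, with every treated patient counted. In Cohort A the 83% does not reproduce (85.8% with 12 patients), and the half-width is slightly above the stated ±14%. Neither affects this point.

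**2. Cohort A under the written rule.** Patients with a dose of both drugs: 0 of 12. With n = 0 the detection probability is 0 and no interval exists. No assumption is needed.

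**3. Cohort B: chance that the rule removes someone.** Let q be the chance that a patient starts nivolumab and never receives ipilimumab. The documents do not give q; the values below are assumptions. The chance of losing at least one of n patients is 1 − (1 − q)^n.

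| q | n = 8 | n = 25 |
|---|---|---|
| 0.5% | 4% | 12% |
| 1% | 8% | 22% |
| 2% | 15% | 40% |
| 5% | 34% | 72% |

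**4. Cohort B: effect if exactly one patient is lost (assumed).**

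| Situation | All treated | Written rule |
|---|---|---|
| Hers is the only such event, full cohort | 1/25 = 4.0%, 90% upper bound 17.6% | 0/24 = 0%, upper bound 11.7% |
| Hers is the only such event, stage 1 | 1/8 = 12.5%, upper bound 47.1% | 0/7 = 0%, upper bound 34.8% |
| Hers is one of three such events | 3/25 = 12.0% | 2/24 = 8.3% |
| An event she did not have | 10/25 = 40.0% | 10/24 = 41.7% |
| Largest 90% half-width | 17.7% | 18.1% |

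The loss of precision is trivial. What matters is that an event can disappear from the summary table.

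**The case against.** The strongest reply is that nobody would apply the rule this way.

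- **Cohort B text.** Section 11.1 gives the 8-week reassessment schedule of Cohort B, while the Cohort A calendar in section 10 has 12 weeks. Cohort A is closed and has its own paragraph in section 13.4 with its own denominators. A sensible analyst would report Cohort A on 12 patients.
- **Loose reading.** Section 13.6.1 says who is included and excludes nobody by name. Its last sentence speaks of study drug in general, and first treatment with both agents could mean the start of the combination regimen.
- **Small effect.** The Cohort B patient is hypothetical. Section 5.8 calls infusion reactions unlikely, nothing supports a rate as high as 5%, and at 0.5% the chance of losing anyone among 25 is 12%. Stage decisions use response only (section 13.1), and individual events are reported in any case (sections 7.3.4 and 7.4).

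The third argument stands and limits the size of the point. The first is a fair account of how the text arose, but the plan supplies no other rule for Cohort A, so the analyst would have to depart from the written one. The second fails against the word each in section 11.1. The study-drug sentence brings in ineligible patients and does not clearly waive the two-drug condition. Even if the loose reading is the intended one, sections 11.1 and 13.6.1 then disagree, and how to treat a nivolumab-only Cohort B patient would be settled after her event is known.

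**Conclusion.** The concern holds and should be fixed. The Cohort A contradiction follows from the text alone: the written set has 0 patients where the plan needs 12. In Cohort B the plan carries two denominators, all treated patients in section 13.4 and patients given both drugs in sections 11.1 and 13.6.1. The difference between them can depend on toxicity. How often that would happen is unknown, so the Cohort B figures illustrate the effect under assumed rates and do not predict it. The harm is confined to summary rates for a secondary endpoint that is only estimated. Neither the response analysis nor the stage decisions are touched.

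**What to change.** Use one definition in sections 11.1, 11.1.1 and 13.6.1, for example:

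> The toxicity set is every patient given any amount of nivolumab or ipilimumab, counted from the start of her first infusion of either agent. Cohort A and Cohort B are reported separately.

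Keep the sentence that retains patients later found ineligible. The definition matches the treated-patient denominators in section 13.4. The cost is one sentence in three places, with no new data and no change to the sample size or to any figure in section 13.4.

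Separately, sections 5.4, 5.8 and the infusion-reaction table in section 6 give different instructions after a grade 3 infusion reaction. These must be reconciled; no view is taken here on which is right.

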13.6.2 Evaluation of Response

All eligible patients included in the study must be assessed for response to treatment, even if there are major protocol treatment deviations or if they are ineligible. Each patient will be assigned one of the following categories: 1) complete response, 2) partial response, 3) stable disease, 4) progressive disease, 5) early death from malignant disease, 6) early death from toxicity, 7) early death because of other cause, or 9) unknown (not assessable, insufficient data). [Note: By arbitrary convention, category 9 usually designates the “unknown” status of any type of data in a clinical database.]

All of the patients who met the eligibility criteria (with the possible exception of those who received no study medication) should be included in the main analysis of the response rate. Patients in response categories 4-9 should be considered to have a treatment failure (disease progression). Thus, an incorrect treatment schedule or drug administration does not result in exclusion from the analysis of the response rate. Precise definitions for categories 4-9 will be protocol specific.

All conclusions should be based on all eligible patients. Subanalyses may then be performed on the basis of a subset of patients, excluding those for whom major protocol deviations have been identified (e.g., early death due to other reasons, early discontinuation of treatment, major protocol violations, etc.). However, these subanalyses may not serve as the basis for drawing conclusions concerning treatment efficacy, and the reasons for excluding patients from the analysis should be clearly reported. The 95% confidence intervals should also be provided.

14 STUDY STATUS UPDATES AND STUDY CLOSURE

14.1 Definitions of Study Status Changes

14.1.1 Temporarily Closed to Accrual

The study status is Temporarily Closed to Accrual when no patient slots are currently available, but there is the possibility that the trial will re-open for accrual (patient slots become available). Sites are not permitted to accrue additional patients until CTEP is notified of Re-Activation.

Study status will need to be changed to Temporarily Closed to Accrual when any of the following criteria are met:

- Sites are notified by CTEP (via Request for Rapid Amendment [RRA]) of changes in the risk/benefit ratio that necessitate changes to the patient Informed Consent document. Requested changes will be specified in the RRA and must be reviewed by the study's IRB.
- CTEP and the lead investigator agree that unacceptable toxicities necessitate a discussion to change the dosing/regimen.
- A protocol-defined benchmark has been achieved (such as an interim analysis before proceeding to the next stage).

14.1.2 Closed to Accrual

The study status is (permanently) Closed to Accrual when no more patient enrollment slots are available, and at least one patient is still actively receiving the study treatment. Sites are no longer permitted to enroll additional patients.

Patient slots are no longer available when the following criteria are met:

- The pre-specified number of evaluable patients has been successfully enrolled, treated, and evaluated.
- The study treatment has failed to meet the pre-specified efficacy goal at the stage 1 interim analysis.
- CTEP and the investigators agree that unacceptable toxicities preclude further enrollment.

14.1.3 Closed to Accrual and Treatment

The study status is Closed to Accrual and Treatment when no more patient enrollment slots are available and no patients are currently receiving the study treatment. Patients may still be enrolled on the protocol only for the purposes of follow-up.

Patient accrual and treatment will be permanently halted when any of the following criteria are met:

- Enrollment was previously closed (study status of “Closed to Accrual”), and no patients are receiving the study treatment.
- CTEP and the investigators agree that unacceptable toxicities preclude further enrollment. In this case, CTEP and the investigators must collaborate to alter the regimen or to halt the study treatment altogether as soon as it can be safely done for patients currently receiving treatment.

CTEP and Theradex **must be notified** when patients are no longer receiving treatment [*i.e.*, when the last patient(s) to be receiving treatment is/are no longer receiving the study regimen for any reason].

14.1.4 Closed to Follow-Up

The study is considered Closed to Follow-Up when all protocol-defined follow-up procedures have been completed for all patients who have not been removed from the study for other reasons. That is, there are no outstanding follow-up procedures to be performed as mandated by the protocol.

CTEP does **not** need to be notified of a status change to “Closed to Follow Up.”

14.1.5 Complete

Study is considered Complete if it has been at least thirty (30) days since the last patient follow-up evaluation.

A citation to a final study report (manuscript, meeting abstract, etc.) is required with the submission of the Protocol Status Update Form to CTEP PIO.

APPENDIX A PERFORMANCE STATUS CRITERIA

| ECOG Performance Status Scale | | Karnofsky Performance Scale | |
|-------------------------------|---|-----------------------------|--|
| Grade | Descriptions | Percent | Description |
| 0 | Normal activity. Fully active, able to carry on all pre-disease performance without restriction. | 100 | Normal, no complaints, no evidence of disease. |
| | | 90 | Able to carry on normal activity; minor signs or symptoms of disease. |
| 1 | Symptoms, but ambulatory. Restricted in physically strenuous activity, but ambulatory and able to carry out work of a light or sedentary nature (e.g., light housework, office work). | 80 | Normal activity with effort; some signs or symptoms of disease. |
| | | 70 | Cares for self, unable to carry on normal activity or to do active work. |
| 2 | In bed <50% of the time. Ambulatory and capable of all self-care, but unable to carry out any work activities. Up and about more than 50% of waking hours. | 60 | Requires occasional assistance, but is able to care for most of his/her needs. |
| | | 50 | Requires considerable assistance and frequent medical care. |
| 3 | In bed >50% of the time. Capable of only limited self-care, confined to bed or chair more than 50% of waking hours. | 40 | Disabled, requires special care and assistance. |
| | | 30 | Severely disabled, hospitalization indicated. Death not imminent. |
| 4 | 100% bedridden. Completely disabled. Cannot carry on any self-care. Totally confined to bed or chair. | 20 | Very sick, hospitalization indicated. Death not imminent. |
| | | 10 | Moribund, fatal processes progressing rapidly. |
| 5 | Dead. | 0 | Dead. |

**APPENDIX B MANAGEMENT ALGORITHMS FOR ENDOCRINOPATHY,
GASTROINTESTINAL, HEPATIC, NEUROLOGICAL, PULMONARY, RENAL, AND
SKIN ADVERSE EVENTS**

Endocrinopathy Management Algorithm

[figure not shown]
Rule out non-inflammatory causes. If non-inflammatory cause, treat accordingly and continue immuno-oncology (I-O) therapy. Consider visual field testing, endocrinology consultation, and imaging.

Patients on IV steroids may be switched to an equivalent dose of oral corticosteroids (e.g. prednisone) at start of tapering or earlier, once sustained clinical improvement is observed. Lower bioavailability of oral corticosteroids should be taken into account when switching to the equivalent dose of oral corticosteroids.

GI Adverse Event Management Algorithm

[figure not shown]
Rule out non-inflammatory causes. If non-inflammatory cause is identified, treat accordingly and continue I-O therapy. Opiates/narcotics may mask symptoms of perforation. Infliximab should not be used in cases of perforation or sepsis.

Patients on IV steroids may be switched to an equivalent dose of oral corticosteroids (e.g. prednisone) at start of tapering or earlier, once sustained clinical improvement is observed. Lower bioavailability of oral corticosteroids should be taken into account when switching to the equivalent dose of oral corticosteroids.

Hepatic Adverse Event Management Algorithm

Rule out non-inflammatory causes. If non-inflammatory cause, treat accordingly and continue I-O therapy. Consider imaging for obstruction.

[figure not shown]
Patients on IV steroids may be switched to an equivalent dose of oral corticosteroids (e.g. prednisone) at start of tapering or earlier, once sustained clinical improvement is observed. Lower bioavailability of oral corticosteroids should be taken into account when switching to the equivalent dose of oral corticosteroids.

*I-O therapy may be delayed rather than discontinued if AST/ALT \leq 8 x ULN and T.bili \leq 5 x ULN.

**The recommended starting dose for grade 4 hepatitis is 2 mg/kg/day methylprednisolone IV.

Neurological Adverse Event Management Algorithm

[figure not shown]
Rule out non-inflammatory causes. If non-inflammatory cause, treat accordingly and continue I-O therapy.

Patients on IV steroids may be switched to an equivalent dose of oral corticosteroids (e.g. prednisone) at start of tapering or earlier, once sustained clinical improvement is observed. Lower bioavailability of oral corticosteroids should be taken into account when switching to the equivalent dose of oral corticosteroids.

Pulmonary Adverse Event Management Algorithm

[figure not shown]
Rule out non-inflammatory causes. If non-inflammatory cause, treat accordingly and continue I-O therapy. Evaluate with imaging and pulmonary consultation.

Patients on IV steroids may be switched to an equivalent dose of oral corticosteroids (e.g. prednisone) at start of tapering or earlier, once sustained clinical improvement is observed. Lower bioavailability of oral corticosteroids should be taken into account when switching to the equivalent dose of oral corticosteroids.

Renal Adverse Event Management Algorithm

[figure not shown]
Rule out non-inflammatory causes. If non-inflammatory cause, treat accordingly and continue I-O therapy

Patients on IV steroids may be switched to an equivalent dose of oral corticosteroids (e.g. prednisone) at start of tapering or earlier, once sustained clinical improvement is observed. Lower bioavailability of oral corticosteroids should be taken into account when switching to the equivalent dose of oral corticosteroids.

Skin Adverse Event Management Algorithm

Rule out non-inflammatory causes. If non-inflammatory cause, treat accordingly and continue I-O therapy.

Patients on IV steroids may be switched to an equivalent dose of oral corticosteroids (e.g. prednisone) at start of tapering or earlier, once sustained clinical improvement is observed. Lower bioavailability of oral corticosteroids should be taken into account when switching to the equivalent dose of oral corticosteroids.

*Refer to NCI CTCAE v4 for term-specific grading criteria.
